8.5 Prior and Concomitant Therapy

A current version of the World Health Organization (WHO) Drug Dictionary will be used to classify medications by preferred term and WHO Anatomical Therapeutic Chemical (ATC) classification of ingredients. ATC classification level 3 will be used. If level 3 is missing, then level 2 will be used. If level 2 is missing, then level 1 will be used. Any medication given before the day of administration of study drug is considered a *prior* medication. Any medication given on or after the day of administration of study drug is considered a *concomitant* medication. A medication can be considered both prior and concomitant. The most conservative algorithms will be implemented in case a medication has partial start/stop date information.

Descriptive statistics, such as frequency counts and percentages will be provided to summarize the use of medications other than the study drug reported throughout the study. The number and percentage of subjects who received other treatment will be shown by WHO classification of ingredients and by preferred term. No statistical tests will be performed on prior and concomitant medications. All prior and concomitant medications data will be presented in listings.

8.6 Analysis of Efficacy Parameters

8.6.1 *Exploratory Phase, Cross-sectional Analysis*

8.6.1.1 *Analysis of Primary Efficacy Variable*

Quantitative Assessment of Images

A one-way ANOVA will be used to compare the mean flortaucipir SUV_r values between diagnostic groups (AD, MCI, and OCN). The F test in the corresponding ANOVA model

will used to test for the difference in SUV_r values among all diagnostic groups while contrasts within the ANOVA model will be used to perform pairwise comparisons between diagnostic groups.

This analysis will be performed on the global cortical average SUV_r (ie, MUBADA SUV_r) as well as the SUV_r for each brain region.

Due to the obvious age difference, YCN group will not be included in the analysis as described above. A two sample t-test between OCN and YCN will be performed instead, to evaluate the differences between OCN and YCN subjects.

An analysis of covariance (ANCOVA) will be used to compare the mean SUV_r values between diagnostic groups (AD, MCI, and OCN) by amyloid beta status (AB+, AB-), and compare mean SUV_r values between amyloid beta status by diagnosis groups while adjusting for age as a continuous covariate. The least square mean estimates will be provided, and proper contrast will be set to compare the LS mean differences within the ANCOVA models. This analysis will be performed on the global cortical average SUV_r (MUBADA SUV_r) as well as the SUV_r for each brain region.

Descriptive statistics for overall SUV_r values for each brain region will be displayed for each diagnostic group as well as by Amyloid beta status (AB+, AB-).

Scatter plots will be generated for Flortaucipir SUV_r versus diagnostic groups (AD, MCI, OCN, and YCN) and Amyloid Beta status (AB+/AB-) across all subjects.

Qualitative Assessment of Images

Flortaucipir scan visual interpretation results, as explained in section 6.4.1.2 will be summarized by clinical diagnosis and by amyloid status as decided by visual interpretation of florbetapir scans. Except for YCN, the overall association of frequency by diagnosis groups and by amyloid status will be tested with a Mantel-Haenszel test. Pearson's Chi-squared test, or Fisher's exact test when appropriate, will be used to test for the general association of tau scan interpretation results by amyloid status, and tau scan interpretation results by clinical diagnosis respectively.

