5. INVESTIGATIONAL PLAN

5.1. Overall Design and Plan of Trial

This is a phase 2 cross-sectional and longitudinal observational study that will evaluate imaging characteristics of ¹⁸F-AV-1451 in control subjects and patients with MCI and AD. This study will be conducted in two phases, an exploratory/hypothesis generating phase and a confirmatory/validation phase, which will have separate subjects and analyses. Approximately 230 subjects will be enrolled in the Exploratory Phase of the study: 80 cognitively healthy volunteers, 80 subjects with MCI, 70 subjects with AD. Approximately 20 cognitively healthy volunteers will be ≥ 20 to ≤ 40 years of age. Approximately 60 cognitively healthy volunteers will be ≥ 50 years of age and will be distributed across age deciles (50-59, 60-69, 70-79 and ≥ 80). Approximately 150 subjects with cognitive impairment will be enrolled in the Confirmatory Phase.

All subjects will provide informed consent before starting any study procedures.

For both the Exploratory and Confirmatory Phases, screening assessments may take place over several days and will include demographic information, cognitive testing, safety assessment, and MRI, including both volumetric and standard clinical sequences. Raters administering the cognitive testing will be blinded to the ¹⁸F-AV-1451 scans for subjects in the Confirmatory Cohort. Subjects who qualify for the study will undergo both a florbetapir F 18 PET imaging session and an ¹⁸F-AV-1451 PET imaging session. Some subjects, who are ≥ 50 years of age, in the Exploratory Phase will have the option to participate in cerebrospinal fluid (CSF) collection by lumbar puncture (LP).

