8.1.2. Exploratory Phase, Cross-sectional Component

8.1.2.1. Primary Objective Analysis

ANOVA analysis will be applied to detect the difference between clinical diagnosis groups. If an overall difference is detected, pair-wised comparisons will be conducted. If the pre-requisites of ANOVA test are not met, Kruskal Wallis and Wilcoxon rank sum test will be conducted instead.

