3.1 Exploratory Phase, Cross-sectional Objectives

The primary objective of the cross-sectional component is:

- To compare Flortaucipir imaging results in subjects with AD to subjects with MCI and cognitively healthy older individuals

The secondary objective of the cross-sectional component is:

- To establish a database of cognitively healthy individuals to show the spectrum of Flortaucipir imaging results in cognitively healthy individuals across a range of age strata

Exploratory objectives of the cross-sectional component are:

- To determine whether greater degrees of cognitive impairment correlate with higher Flortaucipir uptake in subjects with an amyloid positive status
- To explore whether tests of specific cognitive domains correlate with regional Flortaucipir uptake
- To explore the relationships between Flortaucipir uptake and biomarkers of neurodegeneration and neurological disease (cerebrospinal fluid (CSF) markers including tau, phospho-tau and beta-amyloid (AB), genetic markers, PET amyloid imaging, and brain atrophy assessed by volumetric magnetic resonance imaging (MRI))
- To expand the Flortaucipir safety database

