4.5 Determination of Sample Size

A total of 230 subjects (80 cognitively healthy volunteers, 80 MCI and 70 AD) will be enrolled in the Exploratory Phase of this study. To explore the Flortaucipir SUVR values across age strata among cognitively healthy subjects, these subjects will be divided into 5 age groups as 20-40 years old, 50-59 years old, 60-69 years old, 70-79 years old and 80 years old or above. There will be 15 subjects in each of the 50 or older age groups and about 20 subjects from age group 20-40 years old. From a preliminary analysis of study T807000, the standard deviation (SD) of SUVR from combination region of interest (ROI) was 0.06 for subjects with low probability of AD. Therefore assuming a 0.06 SD, a sample of 15 subjects will give an approximately 90% probability to observe a 95% confidence interval as accurate as +/-0.04 around the point estimation.

From previous studies, the amyloid positive rate is approximately 50% among MCI patients and approximately 80% from AD subjects. Therefore 80 MCIs and 70 ADs will likely result in 40 amyloid positive MCIs and 56 amyloid positive ADs. Also from study T807000, the combination ROI SUVR difference between CN and AD was 0.39, with a pooled SD of 0.27. Assume a pooled SD of 0.30, a sample of 60 CNs and 56 amyloid positive ADs will give a 90% power to detect a 0.18 difference between the CN and AD groups.

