All values will be summarized by the four diagnostic groups: young cognitively normal (YCN) subjects (healthy volunteers ≥ 20 years of age and ≤ 40 years of age), old cognitively normal (OCN) subjects (healthy volunteers ≥ 50 years of age), patients with AD, patients with MCI, and overall. Frequency distributions including counts and percentages will be included for all categorical outcomes. Summary statistics including mean, standard deviation, median, minimum and maximum values will be presented for all continuous outcomes. Unless otherwise specified, hypothesis testing will be two-sided with type I error rate of 0.05.

All statistical analyses will be performed using SAS® version 9.3 or higher.

7.2 **Adjustments for Covariates**

Not applicable for the primary analyses.

7.3 **Handling of Dropouts or Missing Data**

Dropout subjects will not be replaced in this study. For situations with no rules for handling missing data, the default will be no imputation.

A likelihood-based mixed effects model for repeated measures will be used to handle missing longitudinal follow up cognitive measurements, or flortaucipir SUVr data. The model parameters are simultaneously estimated using restricted likelihood estimation incorporating all of the observed data. Estimates have been shown to be unbiased when the missing data are missing at random and when there is ignorable non-random missing data.

Repeated measures analyses will only use data from visits where the data was scheduled to be collected. When subjects discontinue from the study early, there may be efficacy data measurements at visits where the variables were not scheduled to be collected. These data will appear in listings only.

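### The primary cross-sectional comparison of AD, MCI and older controls has no age term, although controls are recruited to an age quota and patients are not, and no age-adjusted overall contrast is planned

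*SAP*

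**What the plan says.** The objective in SAP 3.1 is overall, not within amyloid strata: "To compare Flortaucipir imaging results in subjects with AD to subjects with MCI and cognitively healthy older individuals".

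- **Primary test.** SAP 8.6.1.1: "A one-way ANOVA will be used to compare the mean flortaucipir" SUVr across AD, MCI and OCN, for the global (MUBADA) measure and each brain region. Protocol 8.1.2.1 agrees: "ANOVA analysis will be applied to detect the difference between clinical diagnosis groups", with rank tests as fallback and no covariate named.
- **Covariates.** SAP 7.2 has one line: "Not applicable for the primary analyses".
- **Control ages.** Protocol 5.1 says that the roughly 60 older controls "will be distributed across age deciles". SAP 4.5 gives the quota: "There will be 15 subjects in each of the 50 or older age groups".
- **Patient ages.** Protocol 5.3.1 requires MCI and AD subjects to be at least 50. There are no bands and no matching to controls.
- **Age elsewhere in the SAP.** Section 8.6.1.1 leaves the young controls out of the ANOVA because of their age. It also plans an ANCOVA of diagnosis by amyloid status, and of amyloid status by diagnosis, "while adjusting for age as a continuous covariate". Section 7.8 splits SUVr at 75 years. The partial correlations (8.6.1.3.1), the ApoE ANCOVA (8.6.1.3.2) and the longitudinal primary model (8.6.2.1) all include age.

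**The concern.** The control age distribution is fixed by quota, and the patient age distribution is whatever recruitment brings. If mean ages differ and SUVr varies with age, the unadjusted group difference contains an age component that the ANOVA cannot separate from diagnosis. The F test and all pairwise contrasts carry it, for MUBADA and for every region.

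The plan uses age in its other principal SUVr models, so the cross-sectional primary test is the exception. SAP 7.2 is also inaccurate as written, because the longitudinal primary model does adjust for age. The contrast most exposed is MCI versus OCN, where the true difference is likely to be smaller than for AD: SAP 4.5 expects about half of MCI subjects to be amyloid negative.

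**Working it through.** **1. The plan's own figure.** SAP 4.5 states 90% power for a difference of 0.18, SD 0.30, with 60 controls and 56 amyloid-positive AD subjects; SAP 7.1 sets two-sided 0.05.

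- SE = 0.30 × √(1/60 + 1/56) = 0.0557.
- Power = Φ(0.18/0.0557 − 1.96) = 0.898. The noncentral t with 114 df gives 0.893.

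The statement reproduces as an unadjusted comparison and is not in dispute.

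**2. Control age spread.** Take the four bands as equally filled and the top band as 80-89 (an assumption). Midpoints are 55, 65, 75 and 85, so the mean is 70 and the SD is √(125 + 100/12) = 11.5 years.

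**3. Bias in the unadjusted difference.** Bias = slope × difference in mean age, and slope = r × SD(SUVr) / SD(age). The documents give neither r nor the age gap. The assumed ranges are r = 0.1 to 0.5 and a gap of 2 to 8 years. SD(SUVr) is 0.06, the SAP 4.5 figure for subjects with a low probability of AD.

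| r | Gap (years) | Slope per year | Bias (SUVr) | Share of 0.18 | Share of 0.39 |
|---|---|---|---|---|---|
| 0.1 | 2 | 0.0005 | 0.001 | 0.6% | 0.3% |
| 0.3 | 5 | 0.0016 | 0.008 | 4.3% | 2.0% |
| 0.5 | 8 | 0.0026 | 0.021 | 11.5% | 5.3% |

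Here 0.39 is the AD-control difference that SAP 4.5 reports from an earlier study. Scaling to the pooled SD of 0.30 instead multiplies each bias by five (0.005 to 0.104, or 2.9 to 57.7% of 0.18). That SD includes the variation among AD subjects, so these figures show only what much steeper patient slopes could do.

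**4. MCI versus OCN.** Assume SD 0.30 applies here too, with 80 and 60 subjects.

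- SE = 0.30 × √(1/80 + 1/60) = 0.051, so the smallest significant difference is 1.96 × 0.051 = 0.10.
- With no true difference, a bias of b gives an error rate of Φ(b/SE − 1.96) + Φ(−b/SE − 1.96): 5.3% for b = 0.008 and 6.8% for b = 0.02.
- A smaller SD in this contrast would make the same bias count for more.

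**5. Effect of adjustment on power.** For the comparison in step 1, assume a within-group age SD of 10 years. Then SE = 0.30 × √(1 − r²) × √(1/60 + 1/56 + d²/(114 × 10²)), where d is the age gap.

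- r = 0, d = 8: SE 0.0601, power 0.850.
- r = 0.3, d = 5: SE 0.0548, power 0.907.
- r = 0.5, d = 0: SE 0.0483, power 0.962.

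The unadjusted value on the same approximation is 0.898, so adjustment can gain or lose power.

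**6. Whether the existing ANCOVA closes the gap.** It compares diagnoses by amyloid status, which is a different question from the overall objective in SAP 3.1. At the planning rate of 80% amyloid positive, only 70 × 0.20 = 14 AD subjects would be in the amyloid-negative stratum.

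**The case against.** Age is not ignored. The age-adjusted ANCOVA stands under the same primary-variable heading, on the same outcomes, and the power statement itself refers to amyloid-positive AD. SAP 7.8 adds the split at 75, SAP 8.4 tabulates age by diagnostic group, and Protocol 8.1.2.3 foresees subgroup or covariate analyses by age. The phase is hypothesis-generating, and the protocol names ANOVA for this objective. All of this stands and limits the seriousness of the point. None of it yields a pooled age-adjusted AD, MCI and OCN contrast: a table of ages shows an imbalance without correcting it, and a split at one cut-point is only a coarse control.

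Three stronger readings are tempting, and the documents do not support them.

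- **That the age quota itself biases the comparison.** It does not. Controls and patients share the same lower limit, and an even spread does not imply a different mean age. A gap is possible, not shown.
- **That the bias could reach about a fifth of the planning difference among controls.** A slope of 0.005 SUVr per year over 8 years gives 0.04, or 22% of 0.18. Over the control bands that slope implies an age-driven SD of 0.005 × 11.5 = 0.058 against 0.06, a correlation of about 0.96. This check has its own limit: 0.06 comes from an earlier study whose age range and relation to the MUBADA measure are not given, and patient slopes may differ.
- **That omitting age necessarily costs precision.** Step 5 of the working shows that it depends on the age correlation and the imbalance.

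**Conclusion.** The point holds in a limited form. The primary cross-sectional model has no age term, the design does not make the groups' ages comparable, and no age-adjusted version of the overall comparison is planned. Neither the size nor the direction of the bias can be taken from the documents. On the assumptions scaled to the control SD, it is about 0.001 to 0.02 SUVr. A bias of that size would not explain an AD-control difference near 0.39; it could matter for a small MCI-OCN difference. Steeper slopes in patients would raise these figures.

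The sample size statement is sound. The case for change rests on protection against bias and on consistency with the SAP's other models, not on an assured gain in power. It should be made, but the exploratory phase does not fail without it.

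**What to change.** - In SAP 8.6.1.1, make the primary model an ANCOVA with diagnosis (AD, MCI, OCN) and continuous age, with contrasts on age-adjusted least squares means for MUBADA and each regional SUVr. State that this model is primary and that the ANCOVA by amyloid status is a further analysis.
- Keep the unadjusted one-way ANOVA as supportive.
- Check the diagnosis-by-age interaction, and say in advance how results will be shown if a common slope does not fit.
- Correct SAP 7.2 to name age as a covariate in both the cross-sectional and longitudinal primary models.
- Record the departure from Protocol 8.1.2.1 in SAP 5.2.

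Cost: SAP text and one degree of freedom. Age is already derived for every subject (SAP 6.3), so no new data are needed, and the central case in the working needs no larger sample. The price is a common-slope assumption and a possible small loss of power if ages are imbalanced but only weakly related to SUVr (0.850 against 0.898 in the least favourable case computed).

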5.2 Changes from the Analyses Planned in the Protocol/CIP

The protocol was amended (version 07 August 2015, Amendment 2). In this amendment the study was divided into two phases, exploratory (first) phase and confirmatory (second) phase. Currently, this SAP provides the planned analyses for the exploratory (first) phase of the study.

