6.4 Efficacy Variables

6.4.1 Primary Efficacy Variable(s)

6.4.1.1 Quantitative assessment of images for Flortaucipir (SUVr based)

For the Flortaucipir image, standard uptake value ratios (SUVr) will be calculated to estimate tau load globally and for each individual region. For global assessment, a target region derived statistically with a Multiblock Barycentric Discriminant Analysis (MUBADA) method will be used; at individual region level, VOIs determined in the AAL atlas masked to exclude white matter and CSF for parietal, temporal, occipital, anterior hippocampal parahippocampal and fusiform gyri will be applied. For all SUVr value calculations, a selected white matter region derived using a parametric estimated signal reference intensity (PERSI) method will be used as reference region.

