8.6.2 Exploratory Phase, Longitudinal Analysis

8.6.2.1 Analysis of Primary Efficacy Variable

Mixed Model Repeated Measures for Evaluation of Flortaucipir SUV_r over time

Descriptive summary statistics for Flortaucipir SUV_r will be provided by amyloid beta status (AB+, AB-) at baseline, 9 month, and 18 month across all subjects.

Change from baseline for Flortaucipir SUV_r will be estimated using repeated measures models for all subjects except for YCN subjects (who do not have follow-up flortaucipir scans at 9 months and 18 month). Due to the concern of unequal variance for flortaucipir SUV_r changes by amyloid status, the model will be run for AB+ subjects only, and for AB- subjects only separately. For this analysis, time will be considered to be categorical variable. A mixed model will be run with MUBADA SUV_r change from baseline as dependent variable, baseline MUBADA SUV_r and age, and visit as independent variables. In order to appropriately model the within subject covariance, the covariance structure must be pre-specified. Each model should be fit using the unstructured covariance structure. If this structure does not converge, covariance structure in the order as auto-regressive, Toeplitz structures and the compound symmetry will be used.

The LS means of MUBADA SUV_r change at each visit from the model will be displayed along with the corresponding 95% confidence intervals. In addition, p-values will be

provided for testing that whether or not the LS means at each visit is significantly different than zero.

Spaghetti plots will be generated to display the relationship of Flortaucipir SUVr change across the follow up visits, by each subject. The plot will use MUBADA SUVr as y-axis, subjects' age at each visit as x-axis, and color code according to amyloid status.

Explore Factors Associated with Flortaucipir SUVr Change using Multivariate Analysis

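### The primary cross-sectional ANOVA draws every pairwise test from one residual variance, although the pilot figures suggest that SUVr spread differs widely between diagnostic groups

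*SAP*

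**What the plan says.** SAP 8.6.1.1 specifies a one-way ANOVA of flortaucipir SUVr on AD, MCI and OCN. The F test covers the overall difference, and "contrasts within the ANOVA model will be used to perform pairwise comparisons between diagnostic groups". The analysis is run on MUBADA SUVr and repeated for each brain region. SAP 7.6 makes no multiplicity adjustment. An ANCOVA by amyloid status, adjusted for age, follows without any statement about unequal variance. Young controls (YCN) are handled separately: "A two sample t-test between OCN and YCN will be performed instead", without saying whether variances are pooled.

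SAP 4.5, like Protocol 8.1.1.1, gives two pilot figures for spread. The combination-ROI SD "was 0.06 for subjects with low probability of AD", and "the combination ROI SUVR difference between CN and AD was 0.39, with a pooled SD of 0.27".

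Protocol 8.1.2.1 has a rule that the SAP does not repeat: "If the pre-requisites of ANOVA test are not met, Kruskal Wallis and Wilcoxon rank sum test will be conducted instead". No check or trigger is given. SAP 5.2, the section for changes from the protocol's analyses, does not mention it.

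The longitudinal section, SAP 8.6.2.1, does react to unequal spread. It opens its justification with "Due to the concern of unequal variance for flortaucipir" SUVr change by amyloid status, and fits amyloid-positive and amyloid-negative subjects separately.

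**The concern.** A contrast inside an ordinary ANOVA uses the residual variance averaged over all three groups, including the group that is not in the contrast. If controls are tight and patients are spread out, the controls pull the average below what applies to AD vs MCI, so that standard error is too small. The AD group pulls it above what applies to MCI vs OCN, so that standard error is too large.

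Comparing AD with MCI and with older controls is the primary cross-sectional objective. The first error makes AD vs MCI look more certain than it is. The second can hide a real difference between MCI and controls.

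**Working it through.** **1. The plan's own figures.** With 60 CN, 56 amyloid-positive AD, SD 0.30 and difference 0.18: SE = 0.30 × √(1/60 + 1/56) = 0.0557, and 0.18/0.0557 = 3.23. Power is 89% (noncentral t) to 90% (normal), against the stated 90%. With n = 15 and SD 0.06, the chance that the 95% CI half-width is at most 0.04 is 88%, against a stated figure of approximately 90%. Both are reproduced. The power calculation assumes a common SD of 0.30.

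**2. AD spread implied by the pilot.** Take the pilot CN as the low-probability subjects (SD 0.06). Let r be the pilot CN:AD ratio, which is not given, and p = r/(1+r).

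- If 0.27 is a within-group pooled SD: AD SD = √[(1+r)·0.27² − r·0.06²].
- If 0.27 is the SD of the combined sample, including the 0.39 mean difference: AD SD = √{[0.27² − p(1−p)·0.39² − p·0.06²]/(1−p)}.

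| r | Within-group reading | Combined-sample reading |
|---|---|---|
| 0.5 | 0.328 | 0.238 |
| 1 | 0.377 | 0.257 |
| 2 | 0.460 | 0.332 |

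Divided by 0.06, these are ratios of 4.0 to 7.7.

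**3. One case in full.** n = 60/80/70 (OCN/MCI/AD); SDs 0.06 / 0.22 (assumed) / 0.377.

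MSE = (59·0.06² + 79·0.22² + 69·0.377²)/207 = 0.0669, root 0.259. Model SE = √[MSE(1/nᵢ + 1/nⱼ)]; true SE = √(sᵢ²/nᵢ + sⱼ²/nⱼ).

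| Contrast | Model SE | True SE | Ratio | Type I, pooled | Type I, Welch |
|---|---|---|---|---|---|
| AD–MCI | 0.0423 | 0.0513 | 0.82 | 10.7% | 5.1% |
| MCI–OCN | 0.0442 | 0.0258 | 1.71 | 0.1% | 5.1% |
| AD–OCN | 0.0455 | 0.0457 | 1.00 | 5.3% | 5.1% |

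Type I error is simulated on normal data, two-sided 5%, 207 df for the pooled contrast.

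**4. Range.** The MCI SD is not in the documents and is assumed throughout.

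| OCN SD | MCI SD | AD SD | AD–MCI | MCI–OCN |
|---|---|---|---|---|
| 0.06 | 0.15–0.30 | 0.257–0.377 | 9.2–11.3% | 0.0–2.0% |
| 0.10 | 0.15–0.30 | 0.27–0.377 | 8.8–10.7% | 0.0–2.2% |
| 0.15 | 0.15–0.25 | 0.27–0.30 | 8.2–8.5% | 1.0–1.6% |
| 0.20 | 0.25 | 0.30 | 7.1% | 2.5% |
| 0.30 | 0.30 | 0.30 | 5.1% | 5.1% |

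In the first row AD–OCN runs from 1.0% to 7.4%, so it has no fixed direction, and Welch gives 4.8–5.2% for all pairs.

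**5. Power, MCI vs OCN.** The assumed true difference is 0.08, which is not in the documents.

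| OCN / MCI / AD SD | Pooled | Welch |
|---|---|---|
| 0.06 / 0.20 / 0.27–0.377 | 42–70% | 92% |
| 0.06 / 0.30 / 0.27–0.377 | 32–48% | 63–64% |
| 0.20 / 0.25 / 0.30 | 44% | 55% |

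**6. Side analyses.** A pooled t-test of OCN (60) against YCN (20), with OCN SD assumed 1.5 to 2 times the YCN SD, has type I error of 1.8% to 0.8%. The protocol's Wilcoxon test, at equal means and OCN SD 0.06 in three scenarios, gives 5.2–6.5% for AD–MCI, 5.1–5.8% for MCI–OCN and 6.8–7.1% for AD–OCN.

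**The case against.** The strongest reply is that the protocol's rank-test rule still applies, since the SAP never withdraws it. A spread ratio of 4 or more would be hard to miss, and with Wilcoxon the two distortions largely disappear. That is right if the rule is applied. But it has no trigger, the SAP is silent on it, and two analysts could properly report different p-values. Wilcoxon also does not test mean SUVr, which is what 8.6.1.1 sets out to compare.

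Second, the pilot SDs come from a combination ROI. In the SAP, "a target region derived statistically with a Multiblock Barycentric Discriminant Analysis (MUBADA) method will be used", with a white-matter reference. The 0.06 describes low-probability subjects, while OCN spans all ages from 50 and is not restricted by amyloid status, so its SD may well be larger. This stands as a limit on size: at 0.25/0.27/0.30, AD–MCI falls to 5.9%.

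Third, the power loss depends on the difference chosen. With SDs 0.06/0.22/0.33 and an MCI–OCN difference of 0.14, both methods exceed 98% (99.0% against 99.97%). AD vs OCN, the only comparison that was powered, would be detected either way at the pilot difference of 0.39. Both points stand.

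Fourth, the ANCOVA text can be read as separate fits by amyloid status, which would allow for part of the unequal spread, and the concern in 8.6.2.1 is about SUVr change, not baseline SUVr. Neither touches the one-way ANOVA.

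**Conclusion.** The concern holds. As written, 8.6.1.1 uses one residual variance for all pairwise tests, and the only spread figures in the documents point to markedly unequal groups. AD vs MCI then rejects too often, about twice the nominal rate if the pilot SDs carry over. MCI vs OCN is conservative and can lose up to about half its power for a modest difference. AD vs OCN is less affected, in either direction.

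The direction was the same in every unequal-SD case run, including MCI wider than AD. The size rests on an assumed MCI SD, on unknown pilot group sizes, on reading the pilot CN as the low-probability subjects, and on combination-ROI SDs transferring to MUBADA SUVr. Because the phase is exploratory and group descriptives will show the spread, this is a change that should be made for correct reported inference. It does not threaten the confirmatory test.

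**What to change.** - In SAP 8.6.1.1, replace the ordinary ANOVA with Welch's ANOVA and Welch (Satterthwaite) pairwise tests. A mixed model with residual variance by diagnosis (PROC MIXED, REPEATED / GROUP=) and Kenward-Roger degrees of freedom serves the same purpose.
- In the amyloid ANCOVA, say whether it is one model or separate fits. Let the residual variance differ by diagnosis-by-amyloid cell. State a minimum cell size below which variances are grouped by amyloid status only; the plan's 80% positive rate implies about 70 − 56 = 14 amyloid-negative AD subjects.
- Name the Welch t-test for OCN vs YCN.
- In 8.6.1.1 and 5.2, state whether this replaces the Kruskal-Wallis/Wilcoxon rule of Protocol 8.1.2.1. If that rule stays, state what triggers it.

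The cost is a few lines of SAP text and SAS code, slightly fewer degrees of freedom, and a larger standard error for AD vs MCI. If the variances prove equal, almost nothing is lost.
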